9.6. Study Drug Accountability

Study drugs will only be used as directed in the protocol. Study personnel will account for all vials of study drugs received, dispensed and used for each subject, and vials returned. The date and time of reconstitution and dilution will be recorded. Used vials should be traceable back to the subject. The Investigator is responsible for the study drug accountability, reconciliation, and record maintenance.

9.7. Study Drug Disposal

Unused, partially used and empty vials will be stored until the Sponsor or sponsor representative instructs the site to return or dispose of the vials. Unused supplies will be returned or disposed of using appropriate documentation according to International Conference on Harmonization-Good Clinical Practice (ICH-GCP), local requirements, applicable Occupational Safety and Health Administration and Environmental Protection Agency regulations, and applicable study-specific procedures.

10. PHARMACOKINETIC, PHARMACODYNAMIC AND RADIOLOGIC ASSESSMENTS

10.1. Sample Collection

Multiple blood samples will be collected from a venous access which is different and on an alternative limb than the site where study drug has been administered. The blood samples will be processed for a determination of whole blood levels of rapamycin, serum levels of SEL-037, uricase activity, serum uric acid levels, antibody (anti-PEG, anti-pegsiticase and anti-uricase) levels, inflammatory marker assessments and T-cell recall assessments according to the procedures in the study laboratory manual and in Section 1.1 (the schedule of events by cohort).

For Part C (Cohorts 13, 15, and 17), at each timepoint specified in the schedule of events (Section 1.1, Table 5), 2 blood samples will be collected for sUA measurement. One sample will be stored and shipped under ambient temperature and one sample will be stored and shipped under frozen conditions. Refer to the Laboratory Manual for details about sample handling.

The target blood collection time for the follow-up visits will be approximately the same time of day as the start of study drug dosing. Blood draws should be collected as close to the times specified, as possible. The acceptable window of collecting samples is:

- All dosing day (Treatment Periods 1, 2, 3, 4 and 5 Day 0) samples: target collection time \pm 5 minute window
- Follow-up visit (Treatment Periods 1, 2, 3, 4 and 5 Day 1): the target collection time \pm 2 hour window from D0 0 hour
- Follow-up visits (All except Day 1): the target collection time \pm 8 hour window from D0 0 hour

- Dosing day (Treatment Periods 2, 3, 4 and 5, Day 0) and EOS visit: target day \pm 1 day window
- Infusion reaction labs \pm 5 minute window

The actual date and time that blood samples were drawn will be captured.

10.1.1. Additional Observational Visit

We have noted in the open label portion of the SEL-212/101 clinical trial and the initial portion of this SEL-212/201 clinical trial a persistent and beneficial effect on serum uric acid (sUA) when subjects are given SEL-212. This effect had persisted beyond 30 days in 17 of 31 subjects as of November 28, 2016. Based on these results, our goal is to follow subjects in Cohorts 3-8, 10, 11, and 12 beyond the current protocol Treatment Period 5, Day 30 Visit so that we may monitor and characterize the continued effect of SEL-212. Since there is a lag between lab results and the visits we would propose to see the subject for an additional visit if the sUA at the Treatment Period 5 Day 21 (Visit 32) is below 6 mg/dL. The additional visit would be 60 ± 1 days after the Treatment Period 5 Day 0 dosing day (Visit 28) at which time we would have the value of the sUA for the Day 21 (Visit 32) visit and their end of study visit (EOS P5 Day 30) value. The beneficial effect on the sUA is an unexpected, positive event which is beneficial to the subject and would likely be beneficial to the projected treatment population in the future.

In Part C (Cohorts 13, 15, and 17), subjects will be followed as described above.

Blood samples will be taken at the observational visits for assessments that will include: serum uric acid, and serum samples for anti-pegsiticase, anti-uricase and anti-PEG.

10.2. Analytical Procedures

Serum samples for SEL-037, for uricase activity and for uric acid determinations and whole blood samples for rapamycin determinations will be measured by validated methods. Serum samples for antibody (anti-PEG, anti-uricase, and anti-pegsiticase) determinations will be measured by validated methods. Procedures for processing samples will be included in the Study Manual.

Anti-pegsiticase, anti-uricase and anti-PEG samples will be sampled as per the schedule of events. At minimum, the samples to be analyzed will include the Day 14 and pre-dose samples for each treatment period as well as the Day 7, 14, 21 and EOS/Early Termination visit for the final treatment period for each subject.

10.3. Pharmacokinetic Assessments

The following PK parameters will be calculated on SEL-037, uricase activity and SEL-110 and assessed: the maximum observed serum concentration (C_{max}), the time at which C_{max} occurred (T_{max}), area under the serum concentration-time curve from time 0 to the time of last quantifiable concentration (AUC_{last}), area under the serum concentration-time curve from time 0 to infinity

(AUC_{inf}), the terminal elimination rate constant (K_{el}), terminal half-life ($t_{1/2}$), serum clearance of drug (CL), and apparent volume of distribution at equilibrium (V_{ss}).

10.4. Radiologic Assessments

Dual energy computed tomography (CT) scans will be performed as an exploratory measure for at least 2 subjects in Cohorts 10, 11, and 12 during the screening interval, between Days 21-28 of Treatment Period 3 (Visit 20-Visit 21), and between Days 21-30 (inclusive) of Treatment Period 5 (Visit 32) or at Early Termination to investigate changes to uric acid deposits. In addition, in any cohorts reopened for enrollment, at least 2 newly enrolled subjects per cohort will undergo DECT during the screening interval, between Days 21-28 of Treatment Period 3 (Visit 20-Visit 21), and between Days 21-30 (inclusive) of Treatment Period 5 (Visit 32) or at Early Termination to investigate changes to uric acid deposits.

In Part C, dual energy CT scans will be performed for Cohorts 13, 15, and 17 as described above. Procedures for the dual energy CT scan and analysis can be found in the study procedure manual.

10.5. Inflammatory Marker Assessments

Assessments of inflammatory markers will be performed as an exploratory measure for all subjects enrolled in each cohort at the predose visit for Treatment Period 1 (Visit 4/Day 0) and one additional inflammatory marker sample is to be collected for Treatment Period 5 – this may be collected at Visit 32/Day 21, between Visit 32/Day 21 and the EOS Visit, or at the EOS Visit/Day 30, or at Early Termination to investigate changes to inflammatory markers. No inflammatory marker assessments will be performed on subjects who have received their first treatment period dose under prior protocol versions not subject to inflammatory marker assessments. Procedures for the assessments and analysis can be found in the study procedure laboratory manual.

In Part C (Cohorts 13, 15, and 17), assessments of inflammatory markers will be performed as an exploratory measure for all subjects at the predose visit and day 7 visit for all Treatment Periods 1-5 and one additional inflammatory marker sample is to be collected near the end of Treatment Period 5 – this may be collected at Visit 32/Day 21, between Visit 32/Day 21 and the EOS Visit, or at the EOS Visit/Day 30, or at Early Termination to investigate changes to inflammatory markers.

10.6. T-cell recall Assessments

Assessments of T-cell recall responses to pegsiticase will be performed as an exploratory measure for all subjects in each cohort to investigate changes to T-cell recall response to pegsiticase. Assessments will be performed for each subject at 3 time points as per the schedules of events and at Early Term visit. If a predose T-cell recall specimen is not available this will not preclude the drawing of a specimen for T-cell recall at v18, v30 or at Early Term. Procedures for the assessments and analysis can be found in the study procedure manual.

11. ASSESSMENT OF SAFETY

11.1. Safety Parameters

11.1.1. Demographic/Medical History

Demographic and significant medical history will be documented. Medical history will be recorded up to the time of dosing.

11.1.2. Vital Signs

Blood pressure, pulse and respiratory rate, temperature will be assessed at times indicated in the schedule of events \pm 2.5 minutes. Blood pressure and heart rate will be recorded after at least 5 minutes of rest in a sitting position. If a conflict occurs during a visit because of multiple assessments needing to occur at the same time point, the ECG may be performed \pm 30 minutes from the designated time so that the vital signs and the blood draws may occur within the stated parameters.

11.1.3. Weight and Height

Height and weight will be recorded at the Screening Visit. Weight will also be recorded at Day 21 visits for each treatment period, ie. at Visits 8, 14, 20, 26 and 32.

11.1.4. Physical Examination

Physical examinations will be conducted at visits indicated in the schedule of events. Breast, rectal and urogenital exams are not required unless warranted based on the clinical judgment of the subject's medical history or current medical condition. The physical exam should be done by a physician or physician's assistant or similarly qualified individual.

11.1.5. Electrocardiogram (ECG)

ECG will be recorded with the subject in a semi-recumbent position after at least 5 minutes of rest and until 4 regular consecutive complexes are available depending on heart rate. If a conflict occurs during a visit because of multiple assessments needing to occur at the same time point, the ECG may be performed \pm 30 minutes from the designated time so that the vital signs and the blood draws may occur within the stated parameters. ECGs will be recorded at times indicated in the schedule of events. Twelve-lead ECGs will be recorded at paper speed of 25 mm/sec. ECG intervals RR, PR, QRS, QT, QTcB and QTcF will be calculated.

11.1.6. Laboratory Assessments

Fasting blood samples collected as indicated in the schedule of events will include a complete blood count (CBC) with differential, clinical chemistry (serum comprehensive metabolic panel including electrolytes – sodium, potassium, chloride, bi-carbonate, phosphate and magnesium),

lipid panel and coagulation parameters (international normalized ratio (INR), activated partial thromboplastin time (aPTT), fibrinogen) and urinalysis.

Screening tests for glucose-6-phosphate dehydrogenase deficiencies, HbA1c, HIV and hepatitis C will be conducted at the Screening Visit.

The collection date, time, and study day will be documented.

11.1.7. Immunogenicity

Blood samples will be collected per the schedule of events. Procedures for processing samples will be included in the study laboratory manual.

11.2. Adverse and Serious Adverse Events

The Investigator is responsible for the detection and documentation of events meeting the criteria and definition of a non-serious adverse events (AE), serious adverse events (SAE) as provided in this protocol.

11.2.1. Definitions

11.2.1.1. Adverse Event

An AE is any untoward medical occurrence associated with the use of a drug (i.e., study drug) in humans, whether or not considered drug related. An AE can therefore be any unfavorable and unintended sign (including an abnormal laboratory finding), symptom, or disease temporally associated with the use of a drug and does not imply any judgment about causality. An AE can arise with use of any drug or medicinal product.

Subjects will be considered enrolled in the study upon dosing of study drug for the first time. AEs (and thus SAEs) will be collected from the time the subject is dosed (infusion is started) until the end of the End of Study Visit. During the Screening Phase (from time informed consent is signed to immediately before dosing) any clinically significant changes in the subject's health will be recorded in the subject's medical history.

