 - Vitals at (Treatment Period 5, Day 0) predose (T-0), intradose after the start of study drug IV infusion (SEL-037) at 15, 30, 45, 60, 90, 120, and 180 minutes, then at 6 hours; and then at Treatment Period 5, Day 1, 7, 14, 21 and 30 or early termination
 - ECG exam at (Treatment Period 5, Day 0) predose and End of Study Treatment Period 5, Day 30 or early termination.
- Part B - Treatment period 5 - Cohort 3 (0.05 mg/kg SEL-110 + 0.2 mg/kg SEL-037), Cohort 4 (0.05 mg/kg SEL-110 + 0.4 mg/kg SEL-037), Cohort 5 (0.08 mg/kg SEL-110 + 0.2 mg/kg SEL-037), Cohort 6 (0.08 mg/kg SEL-110 + 0.4 mg/kg SEL-037), Cohort 7 (0.1 mg/kg SEL-110 + 0.2 mg/kg SEL-037), Cohort 8 (0.1 mg/kg SEL-110 + 0.4 mg/kg SEL-037), Cohort 10 (0.125 mg/kg SEL-110 + 0.4 mg/kg SEL-037), Cohort 11 (0.15 mg/kg SEL-110 + 0.2 mg/kg SEL-037), and Cohort 12 (0.15 mg/kg SEL-110 + 0.4 mg/kg SEL-037)

- Vitals at (Treatment Period 5, Day 0) predose (T-0), intradose after the start of study drug IV infusion (SEL-037) at 15, 30, 45, 60, 90, 120 and 180 minutes, then at 6 hours; and then at Day 1, 7, 14, 21 and 30 or early termination.
- ECG exam at (Treatment Period 5, Day 0) predose and End of Study Treatment Period 5, Day 30 or early termination.
- Adverse events (AE) and serious adverse events (SAE) starting at dosing. AEs will be graded according to Rheumatology Common Toxicity Criteria, version 2.0. If a severe infusion reaction occurs, a determination of anaphylaxis (Grade 4 reaction) will be based on the National Institute of Allergy and Infectious Diseases (NIAID)/ Food Allergy & Anaphylaxis Network (FAAN) Anaphylaxis Criteria.
- Concomitant medication usage will be recorded throughout the trial.
- Clinical laboratory tests (blood chemistry, hematology including clotting parameters, and urinalysis) per the Time and Events Schedule.
- Immunogenicity samples for anti-PEG antibodies at the Screening Visit and for anti-pegsiticase, anti-uricase, and anti-PEG antibodies at baseline (predose for Treatment Periods 1, 2, 3, 4 and 5), Day 7, 14, and 21 post each treatment for Treatment Periods 1, 2, 3, 4, and 5, and EOS / early termination (Treatment Period 5, Day 30).

Safety (Part C, Cohorts 13, 15, and 17):

Note: Cohorts 14 and 16 are intentionally omitted from this protocol in order to maintain the cohort numbering convention of associating odd numbered cohorts with the 0.2 mg/kg SEL-037 dose.

- Physical exam at the Screening Visit and Treatment Period 5, Day 30/early termination.

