7.2. Subject Exclusion Criteria

1. History of anaphylaxis or severe allergic reactions;
2. History of any allergy to pegylated products, including peginterferon alfa-2a (Pegasys[®]), peginterferon alfa-2b (PegIntron[®]), pegfilgrastim (Neulasta[®]), pegaptanib (Macugen[®]), pegaspargase (Oncaspar[®]), pegademase (Adagen[®]), peg-epoetin beta (Mircera[®]), pegvisomant (Somavert[®]), certolizumab pegol (Cimzia[®]), naloxegol (Movantik[®]), peginesatide (Omontys[®]), pegaptanib (Macugen[®]) and doxorubicin liposome (Doxil[®]);

3. Medications which are known CYP3A4 inhibitors or inducers **MAY** be exclusionary. Patients taking medications that are known CYP3A4 inhibitors or inducers including natural products such as St. John’s Wort or grapefruit juice may be included **ONLY** if they discontinue the medication 14 days before dosing and are able to remain off the medication for the duration of the study.
4. Drugs known to interact with Rapamune such as cyclosporine, diltiazem, erythromycin, ketoconazole (and other antifungals), nifedipine (and other calcium channel blockers), rifampin, verapamil unless they are stopped 2 weeks prior to starting the trial and will not be used during the trial.
5. Women of child bearing potential, Defined as:
 - <6 weeks after surgical bilateral salpingo-oophorectomy with or without hysterectomy
 - Pre or perimenopausal (< less than 24 months of natural amenorrhea)
6. Initiation or change in dose of hormone-replacement therapy for menopausal women less than 1 month prior to the Screening Visit or during the Screening Phase would be exclusionary. If after being on a stable dose of hormone-replacement therapy for one month the patient may be considered for the study if she continues to meet all other inclusion and exclusion criteria
7. Uncontrolled diabetes with baseline HbA1c $\geq 8\%$;
8. Fasting screening glucose greater than 240 mg/dL
9. Fasting triglyceride greater than 300 mg/dl;
10. Fasting LDL cholesterol greater than 200 mg/dl;
11. Glucose-6-phosphate dehydrogenase deficiency;
12. Uncontrolled hypertension: Blood pressure >170/100 at screening and 1 week prior to dosing
13. Individual laboratory values which may be exclusionary
 - White blood cell count less than 3.5×10^9 /L
 - Serum aspartate aminotransferase (AST) or alanine amino transferase greater than 3x upper limit of normal (ULN) in the absence of known active liver disease
 - Glomerular filtration rate less than 40 ml/min/1.73 m²

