7.4. Subject Completion and Withdrawal

7.4.1. Screen Failures

An evaluation of the subject's eligibility occurs from consent through the predose assessments and a subject will not be considered enrolled in the study until dosed with study drug. Any subject that is screened but not dosed will be considered a screen failure and the reason for failure will be documented.

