8.2.3. Gout Flares (Prevention and Treatment)

All subjects that meet all inclusion and exclusion criteria will be given premedication for gout flare prevention. The regimen will begin 1 week prior to the first dosing of study drug and continue for as long as the subject is enrolled in the clinical study. Subjects will be given colchicine 1.2 mg as a single loading dose. Then they will continue with colchicine 0.6 mg QD for the remainder of their participation in the trial. If there is a contraindication to colchicine, the subject will receive ibuprofen 600 mg TID or an equivalent NSAID unless the subject has a contraindication to NSAID. If the subject has a contraindication to colchicine and to NSAIDs then no premedication will be given. The gout flare prevention medication should continue as long as the subject is enrolled in the clinical study. Subjects who began receiving a NSAID as gout flare prevention medication due to a contraindication to colchicine or under a previous version of this protocol should continue to receive the NSAID as long as the subject is enrolled in the study. These medications will be supplied by the clinic.

As gout flares are expected to happen despite the subject receiving preventative premedication they (the gout flare) are to be recorded as an adverse event and treated at the discretion of the investigator to provide adequate patient care. Investigators should consult with the medical monitor if a change in the subject's uric acid lowering medication is needed.

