11.3. Reporting Adverse Events

11.3.1. Adverse Event Reporting Period

The study period during which AEs must be reported is from the time the subject is dosed until the End of Study. During the Screening Phase (from time informed consent is signed up to the time of dosing) any clinically significant changes in the subject's health will be recorded in the subject's medical history.

Investigators are not obligated to actively seek AEs or SAEs in former study participants. However, if the Investigator learns of any SAE, including a death, at any time after a subject has been discharged from the study, and he/she considers the event reasonably related to the study drug, the Investigator should promptly notify the Sponsor.

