12.8.1. Demographic and Baseline Characteristics

Baseline characteristics and demographics will be listed and summarized. Medical history will be listed only.

Extent of exposure to study drug will be listed by dose.

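### A serious event that starts after the first protocol-required step but before the first infusion falls outside SAE reporting

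*Protocol*

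**What the plan says.** Three places in the protocol set the start of collection. Section 11.2.1.1 says "AEs (and thus SAEs) will be collected from the time the subject is dosed (infusion is started", Section 11.3.1 says "The study period during which AEs must be reported is from the time the subject is dosed until the End of Study", and the synopsis has "Adverse events (AE) and serious adverse events (SAE) starting at dosing". For the time from consent to dosing, Section 11.3.1 directs that "any clinically significant changes in the subject's health will be recorded in the subject's medical history".

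Other sections place trial-required steps before that point:

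- **Flare prophylaxis (8.2.3).** "The regimen will begin 1 week prior to the first dosing of study drug". The drug is colchicine, or an NSAID where colchicine is contraindicated. Nothing is given if both are contraindicated.
- **CYP3A4 inhibitors and inducers (7.2, criterion 3).** Users may enter only "if they discontinue the medication 14 days before dosing" and stay off the drug.
- **Drugs that interact with Rapamune (7.2, criterion 4).** Users must stop two weeks before starting the trial. Calcium channel blockers are among the listed drugs.
- **Infusion premedication (8.2.1).** Fexofenadine is taken the evening before and again about 2 hours before the infusion. Intravenous steroid follows about 1 hour before.

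On subjects who do not reach the infusion, Section 7.4.1 says "Any subject that is screened but not dosed will be considered a screen failure". On reporting, Section 12.8.1 says "Medical history will be listed only", whereas SAP Section 7.3 also provides for coded summaries of medical history.

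**The concern.** Subjects who have consented take a new drug, or give up an existing one, because the protocol requires it. The collection rule is tied to the study-drug infusion and not to the first of these steps. If a subject is hospitalised during the run-in, no SAE form is due. If that subject is then not dosed, the record is a reason for screen failure.

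What is at stake is prompt notice to the sponsor and the IRB of serious harm that may come from the trial's own requirements. The question does not concern the accuracy of the estimates for SEL-212.

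**Working it through.** The plan gives no figure to reproduce. The check compares dates and looks for any other route to reporting.

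**1. Is there another route before the infusion?**

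- Section 11.2.1.3 defines an SAE as a kind of AE, so an event that is not collected as an AE cannot become an SAE.
- The 24-hour procedure (11.3.2) and IRB reporting (11.3.4) are both written for SAEs.
- Two provisions reach outside the window. One covers SAEs learned of after discharge and judged related to study drug (11.3.1); the other covers pregnancy (11.2.2.7). Neither covers the run-in.
- Section 11.2.2 encourages subjects to report health changes from consent and has staff ask about them. It does not turn pre-dose changes into AEs.
- Section 11.2.2.6 makes significant laboratory and diagnostic abnormalities reportable, but only in dosed subjects.
- A subject never dosed is outside the safety analysis set (protocol 12.2, SAP 5.2).

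No such route was found.

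**2. How long is the uncovered interval?**

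A completer has four periods of 28 days and then 30 days to the End of Study visit: 4 × 28 + 30 = 142 days of collection.

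- Prophylaxis: 7 / (142 + 7) = 7/149 = 4.7% of the time under required intervention.
- Drug withdrawal: 14 / (142 + 14) = 14/156 = 9.0%, in users of the listed drugs only.

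The two withdrawal criteria have different anchors, dosing and the start of the trial. Under the second, the interval could exceed 14 days.

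**3. How many subject-days?**

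- Whole trial, about 140 subjects (4.6): at most 140 × 7 = 980 subject-days of prophylaxis, fewer if some have both contraindications.
- Still open at version 7.1: Cohorts 11 and 12 at up to 20 each and Part C at up to 40 (6.2), so 20 + 20 + 40 = 80 subjects. This gives at most 80 × 7 = 560 subject-days, unless closed cohorts reopen.
- Withdrawal: the share of users is not stated. Assuming 5%, 10% or 20% of 140 gives 140 × share × 14 = 98, 196 or 392 subject-days.

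**4. What would this mean in events?**

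The documents give no risk for this interval, so the risks below are assumptions only. With n subjects and risk p each, the expected number is n × p and the chance of at least one event is 1 − (1 − p)^n.

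| Assumed p | Expected, n = 140 | At least one, n = 140 | Expected, n = 80 | At least one, n = 80 |
|---|---|---|---|---|
| 0.5% | 0.7 | 50% | 0.4 | 33% |
| 1% | 1.4 | 76% | 0.8 | 55% |
| 2% | 2.8 | 94% | 1.6 | 80% |
| 5% | 7.0 | >99% | 4.0 | 98% |

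**The case against.** The best defence is that the rule is coherent. It appears the same way in all three places, and it fits a primary objective about infusions of SEL-212, with AE endpoints running to 30 days after the last dose (SAP 4.3). Run-in events are not lost either. They are asked about and recorded, screen-failure reasons are documented, screen failures are listed (SAP 7.1), and SAP 7.3 summarizes medical history. All of this stands. It shows that the information is kept, but not that anyone must report a serious event promptly.

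Several stronger readings are tempting and are not supported:

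- **That harm from prophylaxis or withdrawal is never reported as an SAE.** Prophylaxis and the drug restrictions continue through the study. An AE counts whatever its cause, so an event starting after the first infusion is collected.
- **That the safety committee is deprived of its trigger.** Section 6.3.2 convenes the committee on SAEs related or possibly related to study drug, in two or more subjects of one cohort. An event before any study drug would not meet that test even if it were reported.
- **That tolerability of the regimen is judged on a selected group.** The objective is the safety of SEL-212 infusions, not of SEL-212 together with its prophylaxis.
- **That 980 subject-days measures missed harm.** It includes closed cohorts, assumes prophylaxis in everyone and carries no event rate.

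**Conclusion.** The gap is real but narrow. It concerns onset between the first protocol-required step and the first infusion, a span of 7 days for prophylaxis and about 14 days for users of the listed drugs. Within it, a serious event carries no duty of 24-hour reporting to the sponsor or of SAE reporting to the IRB. The number of such events cannot be estimated from the documents, and the table above illustrates assumed risks only. No planned treatment-emergent summary is biased by the rule. The case for change is better safety reporting at little cost.

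**What to change.** In the synopsis and Sections 11.2.1.1 and 11.3.1, collect the following from signed consent, or at the latest from the first protocol-required step, including in subjects who are never dosed:

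- all SAEs;
- non-serious AEs judged related to a protocol-required procedure, drug withdrawal or premedication.

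Keep the treatment-emergent tables on onset at or after the first infusion. In Section 12.8.2 and SAP Section 11.3, replace the statement that every collected AE is treatment-emergent with a rule based on onset date, and add a separate listing of pre-dose events.

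The cost is wording in the protocol and SAP, CRF pages and safety-database handling for screen failures, a few more SAE reports, and one listing. Cohorts already closed will have no matching pre-dose data, so the listing should state when the wider collection began.
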